## Do not use this device:

- With a long sheath with diameter less than 8.5Fr or a short introducer with diameter less than 8.5Fr
- In the coronary vasculature

#### 5.3.4. Contraindications outside the U.S.

Contraindications outside of the U.S. may be different. Centers participating in geographies outside of the U.S. will follow their country specific contraindications for the IntellaNav StablePoint Catheter System based on whether it is considered investigational or commercial in their region. Please refer to the country specific contraindications for additional information in specific regions.

# 6. Study Objectives and Endpoints

The objective of the study is to establish the safety and effectiveness of the StablePoint Catheter and Force Sensing System for the treatment of symptomatic, drug refractory, recurrent paroxysmal atrial fibrillation (PAF). The following endpoints will be evaluated to establish the safety and effectiveness of the StablePoint Catheter and Force Sensing System for the treatment of symptomatic, drug refractory, recurrent PAF.

# 6.1. Primary Safety Endpoint at 30 Days

The primary safety endpoint at 30 days is defined as the safety event-free rate at 1-Month (30 days) post-procedure. Primary safety endpoint definitions are outlined in Table 6-1.

Primary safety events at 30 days will consist of a composite of the following serious procedure and/or device-related adverse events. Events will be counted through 7 days post index procedure or hospital discharge, whichever is later, unless denoted as events counting through 30 days post index procedure.

- Death
- Myocardial infarction (MI)
- Vagal Nerve Injury/Gastroparesis
- Transient ischemic attack (TIA)
- Stroke/Cerebrovascular accident (CVA)
- Thromboembolism
- Pericarditis
- Cardiac tamponade/perforation\*
- Pneumothorax
- Major vascular access complications
- Pulmonary edema/heart failure
- AV block\*\*
- Atrial esophageal fistula\*
- Severe pulmonary vein stenosis (≥70% reduction in the diameter of the PV or PV branch from baseline)\*

\*Atrial esophageal fistula, cardiac tamponade/perforation and severe pulmonary vein stenosis occurring up to 30 days post-index-procedure will count as primary safety endpoint events

\*\*AV block not attributable to medication effect or vasovagal reaction.

Table 6-1: Primary Safety Endpoint Definitions

Terms	Definitions					
Atrioesophageal Fistula	An atrioesophageal fistula is defined as a connection between the atrium and the lumen of the esophagus. Evidence supporting this diagnosis includes documentation of esophageal erosion combined with evidence of a fistulous connection to the atrium, such as air emboli, an embolic event, or direct observation at the time of surgical repair. A CT scan or MRI scan is the most common method of documentation of an atrioesophageal fistula.					
AV block	A conduction disturbance that results in the partial inability of an electrical impulse generated in the atria to reach the ventricles. Refers to AV block not attributable to medication effect or vasovagal reaction.					
Cardiac tamponade/ Perforation	The development of a significant pericardial effusion during or within 30 days of undergoing an AF ablation procedure. A significant pericardial effusion is one that results in hemodynamic compromise, requires elective or urgent pericardiocentesis, or results in a 1-cm or more pericardial effusion as documented by echocardiography.					
Major Vascular access complications	Development of a hematoma, an AV fistula, or a pseudoaneurysm. A major vascular complication is defined as one that requires intervention, such as surgical repair or transfusion, prolongs the hospital stay, or requires hospital admission.					
Myocardial infarction (in the context of AF ablation)	The presence of any one of the following criteria:  (1) detection of ECG changes indicative of new ischemia (new STT wave changes or new LBBB) that persist for more than 1 hour;					
	(2) development of new pathological Q waves on an ECG; (3) imaging evidence of new loss of viable myocardium or new regional wall motion abnormality.					
Pericarditis	Inflammation of the pericardium surrounding the heart. Pericarditis should be considered a major complication following ablation if it results in an effusion that leads to hemodynamic compromise or requires pericardiocentesis, prolongs hospitalization by more than 48 hours, requires hospitalization, or persists for more than 30 days following the ablation procedure.					
Pneumothorax	Collapse of the lung due to an abrupt change in the intrapleural pressure within the chest cavity.					
Pulmonary edema/heart failure	Ineffective pumping of the heart leading to an accumulation of fluid in the lungs. Typical symptoms include shortness of breath with exertion, difficulty breathing when lying flat and leg or ankle swelling. Pulmonary edema/heart failure will be considered a primary safety endpoint event when an intervention is required, such as administering diuretics or a prolonged hospitalization.					
Severe Pulmonary Vein Stenosis	Severe pulmonary vein stenosis is defined as a reduction of the diameter of a PV or PV branch. PV stenosis can be categorized as mild <50%, moderate 50%—70%, and severe ≥70% reduction in the diameter of the PV or PV branch. A severe PV stenosis will count towards the primary safety endpoint if it is confirmed by imaging.					
Stroke/Cerebrovascular accident (CVA)	Rapid onset of a focal or global neurological deficit with at least one of the following: change in level of consciousness, hemiplegia, hemiparesis, numbness or sensory loss affecting one side of the body, dysphasia or aphasia, hemianopia, amaurosis fugax, or other neurological signs or symptoms consistent with stroke.					
	
 
Duration of a focal or global neurological deficit ≥24 hours; OR <24 hours if therapeutic intervention(s) were performed (e.g., thrombolytic therapy or intracranial angioplasty); OR available neuroimaging
 
					

	documents a new hemorrhage or infarct; OR the neurological deficit results in death.					
	
 
No other readily identifiable non-stroke cause for the clinical presentation (e.g., brain tumor, trauma, infection, hypoglycemia, peripheral lesion, pharmacological influences).
 
					
	
 
Confirmation of the diagnosis by at least one of the following: neurology or neurosurgical specialist; neuroimaging procedure (MRI or CT scan or cerebral angiography); lumbar puncture (i.e., spinal fluid analysis diagnostic of intracranial hemorrhage)
 
					
	
 
Stroke: (diagnosis as above, preferably with positive neuroimaging study);
 
					
	
 
Minor-Modified Rankin score <2 at 30 and 90 days
 
					
	
 
Major–Modified Rankin score ≥2 at 30 and 90 days
 
					
Thromboembolism	The blockage of a blood vessel lumen by solid material such as device fragments, blood clot or other tissues that have migrated from another anatomic site.					
Transient Ischemic Attack (TIA)	New focal neurological deficit with rapid symptom resolution (usually 1 to 2 hours), always within 24 hours; neuroimaging without tissue injury.					
Vagal Nerve Injury/Gastroparesis	Vagal nerve injury is defined as injury to the vagal nerve that results in esophageal dysmotility or gastroparesis. Vagal nerve injury is considered to be a major complication if it prolongs hospitalization, requires hospitalization, or results in ongoing symptoms for more than 30 days following an ablation procedure.					

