## 11.1.4. Primary Safety Endpoint at 12 Months

The primary safety endpoint at 12 months consists of a composite of acute and chronic safety endpoint events as defined in Section 6.4. The primary safety endpoint at 12 months will be evaluated by the primary safety event-free rate at 12 months post-procedure, which will be assessed after study completion.

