# Respiratory arrest/distress/insufficiency/dyspnea

- Arrhythmia (new or exacerbated)
- Conduction pathway injury (Complete heart block (transient or permanent), nodal injury, etc.)
- Nerve injury, for example:
  - o Phrenic nerve injury
  - Vagal nerve injury
- Gastrointestinal disorders
- Vessel trauma, including:
  - Perforation
  - Dissection
  - Coronary artery injury
  - Vasospasm
  - Occlusion
  - Hemothorax
- Cardiac trauma, for example:
  - Cardiac perforation/cardiac tamponade/pericardial effusion
  - Valvular damage
  - Stiff left atrial syndrome
- Injury related to tissue damage and/or adjacent structures and/or related structures, for example:
  - Esophageal injury
  - Physical trauma
  - Pulmonary injury
  - Catheter Entrapment
- Fistula, for example:
  - Atrio-esophageal fistula
  - Bronchopericardial fistula
- PV stenosis and its symptoms, for example:
  - o Cough
  - Shortness of breath,
  - o Fatigue
  - Hemoptysis
- Surgical and access complications, for example:
  - Hematoma/seroma
  - o AV fistula
  - o Bleeding

- Pseudoaneurysm
- Pneumothorax
- o Residual atrial septal defect

Injury due to embolism/thromboembolism/air embolism/foreign body embolism

- Cerebrovascular Accident (CVA)/stroke
- Transient Ischemia Attack (TIA)
- Myocardial infarction
- Neurological impairment and its symptoms, for example:
  - Cognitive changes, visual disturbances, headache, motor impairment, sensory impairment, and speech impairment
- Pulmonary embolism
- Asymptomatic cerebral embolism

The potential adverse events may be related to the diagnostic mapping catheter(s) and/or the interventional ablation device(s) and/or the procedure. The severity and/or the frequency of these potential adverse events may vary and may result in prolonged procedure time and/or additional medical and/or surgical intervention, implantation or permanent device such as a pacemaker, and in rare cases, may result in death. Refer to the RF Controller, Irrigation Pump, and other ancillary device instructions for additional potential adverse events related to their use with the IntellaNay StablePoint.

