### 26.2. Definitions

Terms are defined in Table 26-2 below.

Table 26-2: Abbreviations and Definitions

Term	Definition		
Activated Coagulation/Clotting Time	ACT is a test that is used to monitor the effectiveness of high dose heparin therapy.		
Acute Procedural Failure	Failure to achieve acute procedural success in the index procedure or repeat procedure during the blanking period		
Arterial-Venous Fistula	Abnormal communication between an artery and a vein.		
Atrioesophageal Fistula	An atrioesophageal fistula is defined as a connection between the atrium and the lumen of the esophagus. Evidence supporting this diagnosis includes documentation of esophageal erosion combined with evidence of a fistulous connection to the atrium, such as air emboli, an embolic event, or direct observation at the time of surgical repair. A CT scan or MRI scan is the most common method of documentation of an atrioesophageal fistula.		
Attempt Subject	Any subject that signs the consent form, meets eligibility criteria and has any study device inserted into the body but does not receive any RF application with the study device.		
AV block	A conduction disturbance that results in the partial inability of an electric impulse generated in the atria to reach the ventricles. Refers to AV block not attributable to medication effect or vasovagal reaction.		
Blanking Period	90-day period between ablation procedure and the initiation of the Effectiveness Evaluation Period during which up to one additional ablat procedures can be performed and subjects can be prescribed antiarrhythmic drugs as determined necessary by the investigator.		
Cardiac tamponade/ perforation	The development of a significant pericardial effusion during or within 3 days of undergoing an AF ablation procedure. A significant pericardial effusion is one that results in hemodynamic compromise, requires electior urgent pericardiocentesis, or results in a 1-cm or more pericardial effusion as documented by echocardiography.		
Embolism	The sudden blocking of an artery by a clot or foreign material which has been brought to its site of lodgment by the blood current.		
Enrolled Subject	A subject who is eligible for enrollment and signs an informed consent document to participate in the study.		
Hematoma	A localized collection of blood, usually clotted, in an organ, space or tissue, due to a break in the wall of a blood vessel.		

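### The AV block definition in Tables 6-1 and 26-2 covers only partial conduction failure, so read literally it leaves complete heart block out of a primary safety component

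*Combined protocol and SAP*

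**What the plan says.** Section 6.1 lists AV block among the components of the 30-day composite and sends the reader to a table for the meaning of each: "Primary safety endpoint definitions are outlined in Table 6-1". The entry there reads "A conduction disturbance that results in the partial inability of an electrical impulse generated in the atria to reach the ventricles". The glossary in Section 26.2 (Table 26-2) has the same definition apart from one word: "A conduction disturbance that results in the partial inability of an electric impulse generated in the atria to reach the ventricles".

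The composite lists in Sections 6.1 and 6.4 name AV block with no restriction by degree. Their only qualifier is "AV block not attributable to medication effect or vasovagal reaction". Section 6.4 places AV block among the events counted through 7 days or hospital discharge, whichever is later. Section 11.1.4 confirms that the later endpoint includes the early components: "The primary safety endpoint at 12 months consists of a composite of acute and chronic safety endpoint events as defined in Section 6.4".

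In Section 18.1, Table 18-1 lists as an anticipated event "Conduction pathway injury (Complete heart block (transient or permanent), nodal injury, etc". The text after that table names "implantation or permanent device such as a pacemaker" among the possible consequences of adverse events.

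Section 21.2 has an independent Clinical Events Committee (CEC) adjudicate the composite events by reference to Section 6.1, and also all adverse events potentially related to the procedure or the study system.

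**The concern.** A block that is complete is not a partial inability to conduct. Applied as written, the definition would count a serious partial block and pass over the more severe form of the same injury, an injury that the protocol itself anticipates. None of the other components in Sections 6.1 and 6.4 names conduction injury. A complete block that is managed without a further component event would therefore have no other way into the composite.

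The 30-day composite is a condition for both PMA-submission success and overall success (Section 6.6), and the 12-month composite is a condition for overall success. A definition that can only omit events moves the observed event-free rate in the device's favour, and a single-arm comparison with a fixed goal has no control arm in which the same omission would occur. If some adjudicators followed the wording and others followed usual clinical meaning, the count would also be inconsistent.

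**Working it through.** The plan has no figure for AV block to reproduce. The check is a comparison of passages, followed by arithmetic on what one reclassified event is worth.

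**Passages side by side**

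| Place | Wording on AV block | Covers complete block? |
|---|---|---|
| Table 6-1 | partial inability | No, read literally |
| Table 26-2 | partial inability | No, read literally |
| Lists in Sections 6.1 and 6.4 | AV block, no degree stated; medication and vasovagal causes excluded | Not restricted |
| Table 18-1 | complete heart block, transient or permanent | Named as an anticipated event |

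The restriction appears in two tables, so it is not a slip in one place, and no passage widens it. For the 30-day composite the link is explicit, because Section 6.1 cites Table 6-1. For the 12-month composite it is inferred: Section 6.4 does not cite the table, and the link rests on the table's general title, the identical qualifier and the protocol-wide glossary.

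**Value of one event**

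Inputs: n = 299 (Section 11.1.4.2); goals of 90% at 30 days and 89% at 12 months; log-log lower limit, one-sided 95% at 30 days (Section 11.1.1.3) and one-sided 97.5% at 12 months (Section 11.1.4.3). Assumption: no censoring.

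One uncounted case: 1/299 = 0.33 percentage points.

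With e events, S = 1 − e/n, se = √[e / (n(n − e))] / |ln S|, and lower limit L = S^exp(z·se).

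- 30 days, z = 1.645. For e = 21, S = 0.9298, se = 0.2183 and L = 0.9010, which passes. For e = 22, L = 0.8971, which fails.
- 12 months, z = 1.960. For e = 22, S = 0.9264, se = 0.2133 and L = 0.8904, which passes. For e = 23, L = 0.8865, which fails.
- 12 months at the 95% limit that the synopsis gives for both safety endpoints, z = 1.645. For e = 23, L = 0.8933, which passes. For e = 24, L = 0.8895, which fails.

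The safety set also includes ATTEMPT subjects (Section 11.3.1), so n need not be 299. At an assumed n = 310 the boundaries are 22 against 23 events at 30 days and 23 against 24 at 12 months (97.5% limit).

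**Illustration on an assumed rate**

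Suppose that 0.33% to 1% of subjects had a qualifying complete block and that none was counted. Take n = 299, no censoring, and a true event-free rate equal to the goal. The probability of passing is then the binomial probability of at most 21 (30 days) or at most 22 (12 months, 97.5% limit) counted events. It rises from about 4.8% to between 6.9% and 13.6% at 30 days, and from about 2.3% to between 3.4% and 7.2% at 12 months. The 0.33% to 1% range is an assumption with no support in the documents. The figures show sensitivity only and are not an estimate of bias.

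**The case against.** The best defence is that the exclusion hangs on one adjective. Every composite list says AV block without limit by degree, and the only exclusion stated anywhere is for medication effect and vasovagal reaction. Adjudication is a real safeguard: Section 21.2 sends every potentially procedure- or system-related adverse event to the CEC, so a complete block reaches it even if a site thinks that the event falls outside Table 6-1. The members include electrophysiology and/or cardiology practitioners, who would probably count it. It would also be reportable under Section 19.1 and, if procedure- or device-related, would appear in the secondary safety endpoint of Section 11.2.1. Table 18-1 is a broad risk list with many entries that are not composite components, so naming complete block there does not by itself contradict the endpoint.

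Much of this stands, and it rules out three stronger readings that a reader might infer:

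- That the sponsor chose to exclude complete block. The unrestricted lists point the other way, and nothing states such an intent.
- That complete block cannot enter the composite at all. It could do so through procedure-related death, or through heart failure requiring intervention. The accurate statement is that no other component names it.
- That the safety result will be biased. No AV block rate is given, and a one-event boundary exists for any ambiguity in any component.

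What the defence does not do is supply a correct definition. The CEC's remit refers to Section 6.1, which refers to Table 6-1. The CEC charter is not among the documents reviewed. Adverse-event reporting does not feed the tests against 90% and 89%. A pre-specified primary endpoint should not depend on adjudicators setting aside its written definition.

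**Conclusion.** The point holds as a drafting defect in a primary endpoint definition. The literal wording of Tables 6-1 and 26-2 omits complete heart block; this bears explicitly on the 30-day composite and by inference on the 12-month one. Confidence is high about the wording and much lower about any consequence, because the CEC would probably count the event.

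The direction of any error is known: literal use would favour the device. Its size is not known. The 0.33 points per case and the one-event boundaries rest on n = 299 and no censoring. The boundaries move with the number of ATTEMPT subjects, with censoring, and with whether the 12-month limit is 97.5% (Section 11.1.4.3) or 95% (synopsis). The correction should still be made, because the rule as written is wrong in an endpoint that decides study success and the remedy is small.

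**What to change.** In Table 6-1 and Table 26-2, replace *partial inability* with *partial or complete inability*. Keep the exclusion for medication effect and vasovagal reaction, and give the CEC the same text for adjudication. A reference to Table 6-1 in Section 6.4 would also make the 12-month link explicit.

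The cost is a wording change in two tables, with no effect on sample size, significance levels or study procedures. The downside is limited: complete blocks will count only if they are serious, procedure- and/or device-related, within 7 days or hospital discharge (whichever is later), and not due to medication or vasovagal reaction. That may make the observed rate slightly less favourable. If complete block was always meant to count, the edit only removes an ambiguity.

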# 6.2. Primary Effectiveness Endpoint – Acute Procedural Success

The primary effectiveness endpoint of acute procedural success is defined as the achievement of electrical isolation of all PVs using the IntellaNav StablePoint catheter only. Electrical isolation of a PV is demonstrated by entrance block after 20 minutes waiting period. If exit block testing is performed, the PV will only be considered as isolated if both entrance and exit block testing are successful.

# 6.3. Primary Effectiveness Endpoint at 6 Months

The primary effectiveness endpoint at 6 months is defined as the effectiveness event-free rate at 6 months (183 days) post-procedure. If the analysis of the primary effectiveness endpoint at 6 months is not passed, then effectiveness may be re-evaluated via the primary effectiveness endpoint at 12 months, as described in Section 6.6.

Primary effectiveness events at 6 months are defined as:

- Acute procedural failure
  - Failure to achieve acute procedural success in the index procedure or in a repeat procedure during the blanking period.
  - Acute procedural success is defined as the achievement of electrical isolation of all PVs using the StablePoint catheter only. Electrical isolation of a PV is demonstrated by entrance block after 20 minutes waiting period. If exit block testing is performed, the PV will only be considered as isolated if both entrance and exit block testing are successful.

- Use of amiodarone post index procedure
- Use of non-study ablation catheter in the index procedure or in a repeat procedure during the blanking period
- More than one repeat procedure during the blanking period (90 days post index procedure)
- Surgical ablation of Atrial Fibrillation (AF)/Atrial Tachycardia (AT)/Atrial Flutter (AFL) post index procedure
- Documented atrial fibrillation, or new onset of atrial flutter or atrial tachycardia between 91 days and 183 days post index procedure captured by one of the following methods:
  - > 30 seconds in duration recording from the study specific event monitor or Holter Monitor
  - ≥ 10 second 12-lead Electrocardiography (ECG)
- Any of the following interventions for atrial fibrillation, or new onset of atrial flutter or atrial tachycardia between 91 days and 183 days post index procedure:
  - Repeat procedure
  - Electrical and/or pharmacological cardioversion
  - Prescribed any AAD\*
- \*AADs for endpoint will consist of all Class I/III, including Amiodarone, and any Class II/IV medications taken for control of atrial fibrillation (AF)/Atrial tachycardia (AT)/Atrial flutter (AFL) recurrence.

